5.3 Run-in Procedures

N/A

5.4 Contraindications

None, other than pregnancy or unprotected intercourse for females of childbearing potential as Berberine has a potential for causing uterine contractions and miscarriage.

5.5 Concomitant Medications

All medications (prescription and over-the-counter), vitamin and mineral supplements, and/or herbs taken by the participant will be documented on the concomitant medication CRF and will include: 1) start and stop date, dose and route of administration, and indication. Medications taken for a procedure (*e.g.*, biopsy) should also be included. Participants must not take any medicines that are inducers, inhibitors or substrates of select CYP isozymes (see Appendix B) within the past 3 months. Participants must not take over-the-counter berberine during the trial.

5.6 Dose Modification

The initial treatment will be 300 mg TID. Toxicity will be graded according to the NCI CTCAE version 4.0. For those subjects experiencing grade 2 toxicity felt to be due to Berberine, dosage will be successively decreased by 100 mg decrements per dose (*i.e.* take fewer pills) (*note*, given TID dosing, this translates to 300 mg/day decrements). If after one week the participant is still experiencing a grade 2 toxicity related to Berberine with the reduced dose, the dose will continue to be decreased (at one week intervals) until a tolerable dosage is reached (< grade 2 toxicity related to Berberine). Those not tolerating 300 mg/day, will be removed from study, as will those experiencing grade 3 or 4 toxicity (related to Berberine) at any dose. The dose will not be 'interrupted' other than stopping the drug to go off the study.

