3. SUMMARY OF STUDY PLAN

This is a single center, double-blind, randomized, placebo-controlled, pilot study. The goal of this Phase I trial is to determine the safety of Berberine in subjects with UC in clinical remission and maintained with Mesalamine. Pilot information about Berberine's ability to modulate relevant biomarkers at the dose being assessed will also be gathered.

Subjects will be randomized in a double-blind fashion to 300 mg TID Berberine (12 subjects) versus placebo (4 subjects), for 3 months. Two additional participants are anticipated to be accrued (for a total of 18 subjects) to account for an anticipated dropout rate of 10%. In order to keep the numbers in either treatment group as planned, dropouts in either treatment group will be replaced by subjects assigned to that same treatment and gender group. Assuming an accrual rate of approximately 1.5 per month, we expect the study to be completed in 12 months.

Subjects will be enrolled and followed up at Department of Gastroenterology, Xijing Hospital, Xi'an, China. For those subjects experiencing grade 2 toxicity felt to be due to Berberine, the dosage will be successively decreased by 100 mg decrements per dose until resolution (note, given TID dosing, this translates to 300 mg/day decrements). Those not tolerating 300 mg/day, will be removed from study, as will those experiencing grade 3 or 4 toxicity at any dose. Compliance will be assessed by pill counts and diary reviews at monthly clinical visits and by measuring plasma Berberine concentrations at the end of the trial. Subjects whose compliance is below 80% will be removed from study.

Colorectal biopsies and blood samples will be taken at the initial visit (pre-treatment). At the end of the 3-month treatment, subjects will repeat earlier screening assessments to determine the outcomes of the primary and secondary objectives. One month post study, subjects will be contacted by clinical visit to assess symptoms.

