8.3 Off-Agent Criteria

Participants may stop taking study agent for the following reasons: completed the protocol-prescribed intervention, adverse event or serious adverse event, inadequate agent supply, noncompliance, concomitant medications, or medical contraindication. Participants will continue to be followed, if possible, for safety reasons and in order to collect endpoint data according to the schedule of events. Subjects who stop treatment for toxicity reason will be followed until the issue is resolved or stabilized. If the drop-out rate is higher than expected, we will recruit more participants. Participants will not be replaced.

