8.4 Off-Study Criteria

Participants may go 'off-study' for the following reasons:

- Adverse Event
- Death
- Disease Progression
- Lost to follow-up
- Other
- Participant Withdrawal
- Participant Refused Follow-up
- Physician Decision
- Protocol Defined Follow-up Completed
- Protocol Violation
- Study Complete
- Ineligible

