13.7 Evaluation of Toxicity

All participants will be evaluated for toxicity from the time of their first dose of Berberine through day 120 (corresponding to one month after completing the 90 day treatment period).

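### Sections 3 and 5.6 disagree on whether a grade 3–4 removal needs attribution to Berberine, and both end study participation where 8.3, 7.5 and 13.7 continue follow-up, so later safety data may be lost in those with the worst toxicity

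*Combined protocol and SAP*

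**What the plan says.** **Attribution.** Section 3 (Summary of Study Plan): "Those not tolerating 300 mg/day, will be removed from study, as will those experiencing grade 3 or 4 toxicity at any dose". Section 5.6 (Dose Modification) limits the second part to attributed toxicity: "as will those experiencing grade 3 or 4 toxicity (related to Berberine) at any dose". Section 11.1.4 grades relatedness on five levels, and no section says which of them count as related for the purpose of 5.6.

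**Study status.** Sections 3 and 5.6 both speak of removal from the study. Section 5.6 adds: "The dose will not be 'interrupted' other than stopping the drug to go off the study". Section 8.4 opens with "Participants may go 'off-study' for the following reasons" and lists adverse event first.

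Other sections treat the same situation as stopping agent only. Section 8.3 names an adverse event as an off-agent reason, then says: "Participants will continue to be followed, if possible, for safety reasons and in order to collect endpoint data according to the schedule of events". It adds: "Subjects who stop treatment for toxicity reason will be followed until the issue is resolved or stabilized". Section 7.5 follows participants with adverse events for 30 days after the last dose or until resolution, whichever is later. Section 13.7 says "All participants will be evaluated for toxicity", from first dose through Day 120.

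**Who is counted.** Section 5.7.1 makes anyone who received agent for any length of time evaluable for toxicity. Section 13.6 describes an intent-to-treat analysis of all randomized patients, then says that participants are not replaced and that the analysis rests on complete data. Sections 13.2 and 13.4 say that dropouts are replaced within treatment and gender group, to reach 16 evaluable subjects. Dropout is not defined.

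**The concern.** Safety is the primary objective, and the Berberine arm has 12 participants. The two removal rules pick out different people: someone with a grade 3 event judged unrelated leaves under Section 3 and stays on treatment under Section 5.6. Investigators are blinded (6.8), so the attribution that decides this is made without knowledge of the arm.

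The second conflict decides what is observed after agent is stopped. A site that follows 5.6 literally closes the participant's record. A site that follows 8.3 continues the schedule of events. Sections 8.1 and 13.4 place end-of-treatment clinical chemistry under the primary endpoint, so the first course loses primary safety information, and loses it selectively in those with the worst toxicity.

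**Working it through.** **Step 1. What is known at removal.** Removal is triggered by a toxicity that has already occurred. Section 11.1.1 requires every adverse event after consent and baseline to be recorded, and 11.1.2 requires its grade, its attribution and whether the subject dropped because of it. The event is therefore in the data before the participant leaves.

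**Step 2. What is still to come.**

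| Item | Where scheduled | If taken off study before Day 83 |
|---|---|---|
| CBC and chemistry | Screening and Day 90 (7.2, 7.4); none listed at Day 7, 30 or 60 (7.3) or Day 120 (7.5) | No protocol laboratory result after baseline |
| Biopsies, research blood, UCDAI | Screening and Day 90 | No post-baseline value |
| Adverse events | Through Day 120 (13.7) | Observation may end at removal |

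Section 7.4 allows the Day 90 procedures from Day 83. As an illustration, a participant removed on Day 30 would have 120 − 30 = 90 days of the 13.7 window unobserved if the off-study wording prevailed. Under 7.5 alone, follow-up would reach at least Day 30 + 30 = 60, and later if the event had not resolved.

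**Step 3. The plan's own bound.** Section 13.4 uses 3/(n+1) with no events: 3/17 = 0.176 for n = 16 and 3/13 = 0.231 for n = 12. These match the stated 0.18 and 0.23. The exact one-sided 95% bounds, 1 − 0.05^(1/n), are 0.171 and 0.221. Neither stated figure depends on the grade 3–4 rule.

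**Step 4. If the case also left the count.** This needs a further step: the removal is treated as a dropout, replaced under 13.2 and 13.4, and left out under the complete-data sentence in 13.6. The event counts below are assumptions, and a grade 3–4 event is assumed to count as a toxicity, although 13.4 names only grade 2. For x > 0 the bound is the exact (Clopper–Pearson) one-sided 95% upper limit. For 1/13 it is the p that solves (1 − p)^13 + 13p(1 − p)^12 = 0.05.

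| Events in Berberine arm (assumed) | Case left out | Case counted |
|---|---|---|
| 1 | 0/12, bound 0.221 | 1/13 = 7.7%, bound 0.316 |
| 2 | 0/12, bound 0.221 | 2/14 = 14.3%, bound 0.385 |

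**Step 5. Could an event occur?** The chance of at least one among 12 is 1 − (1 − p)^12. The documents give no rate for such events, so p is assumed: 3% gives 0.31, 5% gives 0.46 and 10% gives 0.72.

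**The case against.** The case on the other side is substantial.

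- A reader might infer that the participants who define the primary endpoint are lost, or that the removal rule itself makes the safety denominator depend on outcome. The documents do not support this. The endpoint in 13.4 is a yes/no status per subject, the event precedes removal and is recorded, and 5.7.1 keeps the participant evaluable. None of Sections 3, 5.6, 8.3 or 8.4 tells the analyst to drop anyone.
- Follow-up is provided for. Sections 8.3 and 7.5 follow toxicity to resolution or stabilization, 11.2.3 does so for serious events, Section 8.4 is permissive, and the schedule in 7.1 labels its last column as Day 120 or early termination.
- Section 3 is a summary. Its preceding sentence, on grade 2 toxicity, is already limited to effects thought to be due to Berberine, so a reader could carry that limit forward.

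The first item stands and restricts the point to later data, with loss of the case only conditional. The second shows what the protocol probably intends, but it does not cancel the sentence in 5.6 that ties stopping the drug to leaving the study, and the Day 120 visit in 7.5 lists no laboratory tests. The third is a plausible reading, but the text still has two rules. Section 5.7.1 does not settle the count by itself, because the replacement rule and the complete-data sentence pull the other way.

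**Conclusion.** Both contradictions are in the current text. Sections 3 and 5.6 differ on attribution, and their off-study wording conflicts with 8.3, 7.5 and 13.7.

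The direct consequence is loss of later data in those with the worst toxicity: Day 90 chemistry, Day 90 biopsies and adverse events to Day 120. This assumes that a site acts on the wording of Sections 3 and 5.6 in preference to 8.3.

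Exclusion of the case from the toxicity count is possible but conditional. It requires the replacement or complete-data text in Section 13 to override 5.7.1 and the intent-to-treat sentence. With one assumed event and both applied, the upper bound for the Berberine arm would read 0.22 when it should read 0.32. The point should be settled before the analysis, but no stated sample size or bound is wrong because of it. Which clinical removal rule is right is not judged here.

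**What to change.** 1. The sponsor should reconcile Sections 3 and 5.6 on whether removal for grade 3–4 toxicity requires attribution. This is a clinical decision and no rule is proposed here. If attribution is kept, say which levels of the 11.1.4 scale count as related.
2. Reword Sections 3 and 5.6 so that stopping agent and leaving follow-up are separate events, consistent with 8.3, 7.5 and 13.7. In 8.4, state that an adverse event does not by itself end follow-up.
3. In 13.4, 13.6 and 13.7, state that everyone who took any study agent is counted in the safety analysis through Day 120; that a participant who stops for toxicity stays in the count even if a replacement is enrolled; and that the complete-data sentence does not apply to safety.

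The cost is wording in these sections. No visits or participants are added, because 8.3, 5.7.1 and 13.7 already provide the follow-up and the evaluability.

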5.7 Adherence/Compliance

- 5.7.1 If less than 80% of the dose has been consumed during the study period, the subject will be considered non-compliant. All participants that receive a study agent for any period of time will be evaluable for efficacy and toxicity. Participants will not be replaced.
- 5.7.2 Clinical visits will be made each month to monitor compliance. Pill counts will be performed and patient diary will be reviewed at each clinical visit. Drug levels will be measured in blood on the last day of administration.

6. PHARMACEUTICAL INFORMATION

6.1 Study Agent

Berberine ($C_{20}H_{18}NO_4$, molecular weight 353.36 Da), a natural plant alkaloid, is found in the roots, rhizomes, and stem bark of many plants and has been widely used to treat gastroenteritis and diarrhea in China^{88, 97}. There is increasing evidence that it inhibits carcinogenesis primarily through anti-inflammatory action⁵³. For this study, Berberine isolated from the *Coptidis* rhizome is supplied by Shanghai SINE TianPing Pharmaceutical Co. (Shanghai, China).

The investigational product to be used in the proposed clinical investigation is a film-coated tablet with a yellow core delivering 100 mg Berberine. Tablets allocated for this study met the requirements and standards from the Pharmacopoeia of the People's Republic of China (2010), are >98% pure, and have an expiration date of May 10, 2017 (Shanghai SINE TianPing Pharmaceutical Co. Ltd. Berberine Hydrochloride Testing Report, December 2, 2013). Additional supply with a later expiry date will be made available if the intervention phase of the study has not completed by that time. Matching placebo tablets will also be supplied by Shanghai SINE TianPing Pharmaceutical Co. Ltd.

6.2 Reported Adverse Events and Potential Risks

Berberine is available as a dietary supplement at doses of 100 to 200 mg/day in the US and has been approved by the Chinese Food and Drug Administration (CFDA) for diarrhea at a dose of 300 mg tid. Predominant clinical uses of Berberine include treatment of bacterial diarrhea, intestinal parasite infections, and ocular trachoma infections⁶⁸. Additionally, Berberine has been investigated for treatment of type 2 diabetes, cardiovascular disease, hyperlipidemia, and cancer. In clinical studies for these indications, oral doses as high as 1500 mg Berberine/day for three months were administered^{51, 87, 97, 100}. No severe adverse effects and no significant changes in plasma kidney and liver parameters were observed in any of the studies. Mild to moderate constipation was seen in 3–8% of subjects. In a study using 300 mg Berberine TID for 30 days in patients with acute coronary syndrome, three of the 61 patients discontinued treatment due to abdominal pain, rash, or constipation⁶⁶.

As most Berberine-containing plants are considered uterine stimulants, they should be used with care during pregnancy⁶.

Berberine has not been shown to be genotoxic and does not induce significant cytotoxic, mutagenic, or recombinogenic effects⁶. The intravenous lethal dose for 50% (median) of test animals (LD_{50}) of Berberine sulfate in mice is approximately 25 mg/kg, while intravenous administration of Berberine to dogs at doses up to 45 mg/kg does not produce gross toxic effects.

6.3 Availability

Berberine and matching placebo will be manufactured and supplied by Shanghai SINE TianPing Pharmaceutical Co., Shanghai, China. Berberine and matching placebo will be packaged in bottles containing 120 tablets.

6.4 Agent Distribution

Shanghai SINE TianPing Pharmaceutical Co. will manufacture the Berberine tablets and matching placebo tables and supply them to the clinical site (Department of Gastroenterology, Xijing Hospital, Xi'an, China).

[name], at Shanghai SINE TianPing Pharmaceutical Co, will be contacted for ordering (E-mail: [contact], [contact]).

6.5 Agent Accountability

The Protocol Lead Investigator, or a responsible party designated by the Protocol Lead Investigator, must maintain a careful record of the inventory and disposition of all agents received from Shanghai SINE TianPing Pharmaceutical Co. using the NCI Drug Accountability Record Form (DARF). The Protocol Lead Investigator is required to maintain adequate records of receipt, dispensing, and final disposition of study agent. This responsibility has been delegated to Department of Gastroenterology, Xijing Hospital. The research pharmacist at Xijing Hospital is [name], who can be reached at [contact], [contact].

Include on the receipt record from whom the study agent was received and to whom it was shipped, date, quantity, and batch or lot number. On the dispensing record, note quantities of and dates when study agent was dispensed to and returned by each participant.

6.6 Packaging and Labeling

Berberine and placebo tablets will be packaged, labeled and distributed by Shanghai SINE TianPing Pharmaceutical Co. Ltd, Shanghai, China. Tablets are packaged in 120-count bottles.

Each bottle will be labeled with a one-part label identifying study specific information, such as study title, DCP protocol number, dosing instructions, recommended storage conditions, the name and address of the distributor, randomization number, and a caution statement indicating that the agent is limited by China law to investigational use only and the agent should be kept out of reach of children.

6.7 Storage

The Berberine tablets that will be used in the study are stable when stored at room temperature (15 to 25 °C) in an air-conditioned space for until dispensed to subjects. Once dispensed, the subjects will be instructed to store the drug in their homes protected from light, heat and moisture. If the results of stability tests at any time points are getting close to the limits of specification, we will contact Shanghai SINE TianPing Pharmaceutical Co. Ltd, to prepare a new batch for the clinical trial.

6.8 Registration/Randomization

A study coordinator must forward to Northwestern via the Northwestern Oncology Trials Information System (NOTIS), a signed and complete informed consent and a completed eligibility checklist for each participant identified as eligible to be entered into the study.

All participants must be registered with the Northwestern University Clinical Research Office within 24 hours of enrollment.

After registration, participants will be randomized by the Quality Assurance Monitors at Northwestern Lurie Cancer Center to either treatment with Berberine or placebo. The purpose of the placebo assignment is to allow evaluation of the perception of subtle, sub-clinical effects that might be associated with trial participation. Investigators and participants will be blinded as to the result of randomization. The following people will be un-blinded: The study statistician, the Lurie Cancer Center Quality Assurance Monitors, and the Investigational pharmacist at Xijing Hospital. The study statistician will set up randomization blocks, as previously described.

Full unblinded randomization information will be faxed to Xijing Hospital research pharmacist at: [name]. The clinical research coordinator will receive a blinded Participant ID code for the patient via fax. Participants must not start protocol treatment prior to randomization with Northwestern.

6.9 Blinding and Unblinding Methods

Study participants will receive a prescription, blinded, from the investigational pharmacy at Xijing Hospital. Unblinding will only occur when it is deemed medically necessary and will only take place after consultation with the NCI, DCP Medical Monitor:

DCP Medical /Scientific Monitor
[name] [name], FACS
NCI/Division of Cancer Prevention
[name]
[name]
[contact]
[contact]
Email: [contact]

If the medical monitor is unavailable or if after hours consultation is needed, please contact [name], at [contact], or [contact].

6.10 Agent Destruction/Disposal

At the completion of the investigation, all returned or unused study agent will be disposed of according to institution-specific policy and procedures for handling investigational agents. Both Xijing hospital and Northwestern University will maintain a record of what is destroyed including name of agent, quantity, lot number and expiration date. All records will be maintained for 5 years from when the study is completed.

7. CLINICAL EVALUATIONS AND PROCEDURES

7.1 Schedule of Events

Evaluation/ Procedure	Screening	Randomization	Day 0*	Day 7 (+/- 3 days)	Day 30 (+/- 3 days)	Day 60 (+/- 7 days)	Day 90 (- 7 days)	Day 120 (+/- 7 days) or Early Termination
Informed Consent	X							
Assess Eligibility	X	X						
Medical History	X							
Physical Exam	X			X	X	X	X	
Vital Signs, Height and Weight ¹	X			X	X	X		X
Baseline Symptoms	X							
UCDAI Questionnaire	X					X		
Laboratory Tests ²	X					X		
Rectal Biopsy ³	X					X		
Research Blood Collection ⁴	X					X		
Concomitant Medications	X		X	X	X	X	X	X
Dispense Study Agent		X		X	X			
Pill Count				X	X	X	X	
Review Agent Diary/Record				X	X	X	X	
Adverse Events			X	X	X	X	X	X
Telephone Contact ⁵			X	X				
Collect Study Agent						X		

1. Vital signs assessment is to include pulse, blood pressure, respiration rate, temperature and weight. Baseline assessment must also include height.
2. CBC, ESR, CRP, and Chemistry Panel (White blood count, RBC count, Hemoglobin, Hct, Platelets, Absolute Neutrophil Count, Glucose, Creatinine, Sodium, Potassium, Chloride, SGOT, SGPT, Total Bilirubin, INR). Baseline assessment must include a serum pregnancy test for all women of childbearing potential. Pregnancy test will only be performed at the screening visit.
3. Colonoscopy with 7 biopsies from inflammatory loci (or from regions close to the initial inflammatory area when the patient was first diagnosed). Biopsies taken on day 90 should be ≥ 5 cm distance from the original biopsy sites.
4. Research blood collection: 5ml into purple EDTA tube for plasma and 4ml into red top tube for cytokines.
5. For Day 0, either a telephone contact or an office visit will occur.

* Participant should begin taking the study medication within 7 days of the screening visit

